1. AS-18
2. PANAS
3. digiBP
4. MADRS-S
5. C-SSRS

If participants do not remit but respond (>/=50% decrease on the MADRS from baseline) to treatment by the end of the acute, 5-day treatment series, they may be referred to a TMS clinic or further treatment per their outpatient psychiatrist.

### **6.3 Description of Study Measures**

- a. Montgomery-Asberg Depression Scale-Clinician Rated (MADRS): The MADRS is a ten-item clinician rated questionnaire. Total scores can range from 0 to 60, with higher scores indicating greater severity of depression (0-6 normal range, 7-19 mild depression, 20-34 moderate depression, >34 severe depression). We will utilize this assessment to determine participant's level of depression and consequent eligibility for the trial. We will then subsequently utilize the MADRS daily and at follow up as our primary outcome measure.
- b. Young Mania Rating Scale (YMRS): The YMRS is an 11-item clinician-administered scale used to measure symptoms of mania. Each item is scored from 0-4 with scores of 4 indicating the presence of more severe mania. This scale will be used to monitor symptoms of mania through each day of iTBS treatment.
- c. Clinical Global Impression Scale - Bipolar Disorder (CGI-BP): The CGI-BP is a 3-item clinician rated scale to provide a global rating of severity of manic and depressive

episodes and the degree of change from the immediately preceding phase and from the worst phase of illness. Each item is rated from 1 to 7 (0 = not assessed and 7 = very much worse or severely ill). The CGI-BP will be administered at screening, baseline and visit follow ups for a more global assessment of patient's illness and symptoms.

- d. Affective Self Rating Scale (AS-18): The AS-18 is a 18 item self-rating scale that assess depressive, manic, and mixed affective states. Each symptom is rated from 0 "none" to 4 "very severe". The AS-18 will be filled out at every study encounter: screening, baseline, active study, and follow up.
- e. Positive and Negative Affect Schedule (PANAS): The PANAS is a 20-item self report scale that consists of different words that describe different positive and negative feelings and emotions. Every item is rated from 1 "very slightly or not at all" to 5 "extremely". The PANAS will be filled out screening, baseline, and follow up encounters. A modified PANAS (items 3, 9, 11, 17, 18, 19) will be administered between every stimulation session to assess for any potential shift towards (hypo)mania
- f. Digital Self-Report Survey of Mood for Bipolar Disorder (digiBP): The digiBP is a 6-item digital survey for measuring mood in bipolar disorder. It has three depressive items (depressed mood, fidgeting, fatigue), two manic items (increased energy, rapid speech), and one mixed item (irritability); and recovers two scores (m and d) to measure manic and depressive severity. The digiBP will be filled out at every study encounter: screening, baseline, active study, and follow up.
- g. Montgomery-Asberg Depression Scale-Self Report (MADRS-S): The MADRS-S is the self-report version of the original ten-item clinician rated questionnaire (MADRS). The MADRS-S comprises 9 items rated on a 0-3 point scale which are summed to calculate a total score. This score is then doubled for comparison with the clinician version of the MADRS. The MADRS-S will be filled out at every study encounter: screening, baseline, active study, and follow up.
- h. Columbia Suicide Severity Rating Scale (C-SSRS): The C-SSRS is questionnaire used for suicide assessment. The C-SSRS measures four constructs: the severity of ideation, the intensity of ideation, behavior and lethality. It includes "stem questions," which if endorsed, prompt additional follow-up questions to obtain more information. We will utilize this along with clinical assessment to monitor for participant's suicide risk. The C-SSRS will be filled out at screening, baseline and follow up.

## 7. SAFETY ASSESSMENTS

### **Risk Assessment:**

**TMS:** Extensive published data show that this accelerated theta-burst rTMS protocol in prefrontal cortex is safe and very well tolerated (Sonmez et al., 2019). The most common side effects were mild headache, fatigue, and some discomfort at the stimulation site.

No seizures were observed in any of the above studies. However, very rarely, TMS can induce seizures (17 reported cases to date among tens of thousands of participants treated with rTMS, but few to none if proper safety and enrollment procedures are followed), with a seizure risk at approximately 1:30,000 sessions for traditional high frequency rTMS (Rossi et al., 2009). To minimize the chances of this adverse event, participants with seizure history will be excluded. The FDA has considered studies of standard TMS to be nonsignificant risk (not requiring an IDE).

Another potential immediate risk is that of induction of mania. Although there have been no such cases of mania induced by TBS, there have been at least 13 cases of rTMS-induced mania reported from fixed-frequency rTMS in participants with depression (Xia et al., 2008). The rTMS-induced mania rate reported by Xia et al was 0.84% as compared to 0.73% for sham, which were not significantly different from each other.

Another potential risk is mild pain at the site of stimulation, which occurs during stimulation only, and which wanes with each session. There is also a risk of psychological distress related to this pain, should it occur, though discomfort associated with rTMS is typically mild, and not distressing when participants are reassured it is not dangerous. For participants that continue to experience discomfort with TMS, pre-treatment with acetaminophen, ibuprofen, and/or lidocaine will be allowed as warranted. Participants and treaters will wear earplugs during all treatment sessions. In between sessions, participants will be placed in a relaxing environment to maximize psychological well-being.

**MRI:** Common MRI risks include claustrophobia, localized twitching (not painful) sensation during MRI, and tinnitus after MRI. There are some contraindications that may prevent a participant from having a scan; however, all participants will be screened prior to scanning to evaluate these risk factors. Due to the strength of the magnetic field, contraindications include participants with heart pacemakers, metallic foreign bodies in their eye, and brain aneurysm clips, as the magnetic field may dislodge the metal leading to injury.

Confidentiality: A risk of all clinical studies is that they collect personal information that may be seen by individuals not associated with the study. This could lead to psychological, social, and cultural risks. However, we will use best practice procedures to minimize the potential for breaches of confidentiality. To protect participants' confidentiality, a numerical system will be used as unique identifiers, and identifying information will not be stored with the data. Electronic data will be collected via REDCap, a HIPAA compliant electronic data capture system, maintained in a protected environment in the SAFE Desktop Environment at Johns Hopkins. Secured information linking participant's ID with protected health information will be separated from the unidentified data. All treatment interactions will occur in a closed-door room with specified study personnel. We will have private rooms available for all participant interviews and follow-up interactions. All video meetings will be conducted using the PHI-safe Zoom video meeting interface or comparable platform.

Long-range Risks: No long-range risks associated with TBS or routine MRI have been reported, and none are anticipated for this study.

**Potential Benefits:**

Participants may have reduction and/or remission of depressive symptoms allowing for improved quality of life, engagement, and functioning. This translates to other downstream benefits such as increased societal/economic productivity. Further, this study may give a way for participants to receive rTMS treatment who otherwise would be ineligible given that rTMS treatment is not covered by many insurance carriers. Demonstration of SAINT efficacy may lead to larger real-world clinical trials for both bipolar I disorder but also perhaps other psychiatric conditions.

### **7.1 Methods for Assessing Adverse Events**

Seizure: A physician will be available at all times during treatment to evaluate any participant experiencing a suspected seizure.

Mania: The rTMS parameters used in this study are the least risky because the intervals of stimulation have been shown to be appropriate for theta burst stimulation in the motor system with no adverse outcomes. Moreover, participants' symptoms will be monitored carefully by both members of the research team and clinical staff. The YMRS will be administered daily to check for mania symptoms. If the participant displays an increased YMRS score ( $>/=2$  points) on 2 questions, stimulation will be stopped and patient will be treated for emergent symptoms via increase of their anti-manic agent and other pharmacologic measures as indicated per clinician assessment.

If any of the research team or clinical staff believe that the participant may be showing signs of hypomania/mania, the YMRS will be administered by trained personnel immediately, the researchers will not wait until the daily assessments are conducted. Further, independently, the modified PANAS (items 3, 9, 11, 17, 18, 19) may be administered between every stimulation session to assess for any potential shift towards (hypo)mania. If a significant increase ( $>/=2$  item increase of 2 or more points) is observed, the YMRS will be administered.

**Suicide:** Monitoring participants depressive symptoms will allow the identification of individuals at risk of suicide and therefore the risk of this occurring can be minimized. At screening, baseline, and follow up the C-SSRS will be administered to directly assess suicidal risk. During active study days suicide risk will be screened via the MADRS which has a question to assess suicidal thoughts. Evaluation of the suicidal risk assessments will be made by the research team immediately upon collection of these instruments to determine if any follow-up is needed as described in section 7.2.

## **7.2 Management of Adverse Events**

**Seizure:** In the unlikely occurrence of a suspected seizure, participation will be discontinued and the participants will be provided with a referral to outpatient care. Any seizure that theoretically could occur would likely be self-limited and lead to no residual neurological impairment. Seizures induced by rTMS are rare, brief and don't result in sequelae, with no events of status epilepticus ever being reported (Rossi et al., 2009).

**Mania:** In the event of emergent mania symptoms (defined as an increase of 2 or more points in at least 2 YMRS items), or clinician judgment, treatment will be discontinued and emergent symptoms will be treated by increasing the dose of the participant's anti-manic agent and other pharmacologic measures if necessary as assessed by the onsite clinician.

**Suicide:** If any study personnel believe a participant is at suicide risk, the site PI will be notified immediately and an emergency consultation between them, clinical staff, and the participant will be had. If the study team considers it necessary, the patient will be referred for emergency psychiatric treatment.

## **7.3 Reporting Procedures**

All adverse events occurring in this study will be reported to both local and Central IRBs according to each institutions' IRB policies. Central IRB shall promptly notify the Principal Investigators (PI) of the study as designated on the IRB protocol submission of all IRB decisions and shall make available to the PIs all applicable study related documents

including but not limited to approved protocols, consent forms, surveys, and decision letters.

All adverse events will also be reported to Magnus Medical, who manufacture the TMS device intended for use in this study, via their safety email address ([[contact]](mailto:[contact])).

#### **7.4 Follow up for Adverse Events**

All adverse events will be followed through until the event(s) have resolved, no further action is required, or participant has been transferred to an appropriate level of clinical care. The study team will communicate with the participants' pre-study care team to coordinate care.

## 8. INTERVENTION DISCONTINUATION

Participants are free to withdraw from the study at any time for any reason. Study doctors are to discontinue participants from the study if participants:

- Request early discontinuation or withdraw consent.
- Experience a serious or intolerable adverse event that prevents the participant from continuing.
- In the Investigator's opinion, is experiencing a clinically significant deterioration.
- Conduct a protocol violation, including lack of compliance.
- Are "lost to follow-up" as defined as no response from participant after daily attempts to contact over the planned five day treatment course.
- Encounter other conditions (such as administrative issues or pregnancy).

If a participant discontinues from the study at any time at their own request or at the study clinician's discretion, the reason(s) for discontinuation are to be recorded by the study.

Participants are to continue care with their pre-study care team. If participants do not remit but respond ( $>/=50\%$  decrease on the MADRS from baseline) to treatment by the end of the acute, 5-day treatment series, they may be referred to a TMS clinic. If participants are withdrawn from the study for reasons related to the treatment (typically adverse event within 30 days of last treatment), they will be followed until the event(s) have resolved or no further action is required. The study team will communicate with the participants' pre-study care team to coordinate care.

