#### **Treatment Details:**

Motor threshold: Using single pulse TMS, the scalp position of lowest motor threshold for the left first dorsal interosseous or abductor pollicis brevis muscles will be determined. Resting motor threshold (MT) will be defined by the lowest power setting producing a visible muscle contraction in  $\geq 5$  of 10 trials.

rTMS system and treatment: For this study, we will be using the the MagVenture MagPro X100 rTMS Stimulator System (Magventure A/S, Denmark) equipped with a double-sided MagVenture Cool-B65 coil. A Localite neuronavigation system (Localite GmbH, Sankt Augustin, Germany) will be used to position the TMS coil over the individualized stimulation target at each session. All participants will receive stimulation using iTBS over the LDLPFC (1800 pulses per session). The individualized treatment targets will be produced from structural and functional MRI scans using the software services of Magnus Medical. The targeting approach will be the same as that used in prior publications (Cole et al., 2020, 2022; Williams et al., 2018).

Stimulation intensity will be standardized at 90% of left RMT, adjusted to skull to cortex distance. No further adjustments are needed based on other patient characteristics or conditions. For safety, stimulation will never be delivered above 120% rMT. Sessions will be delivered using the MagVenture MagPro X100 stimulator, with triple-pulse 50-Hz bursts given every 200ms (at 5 Hz).

The iTBS protocol will consist of a 2s train of bursts given every 10 s for a total of 570s (1800 pulses) over the LDLPFC.

If treatment emergent mania occurs (defined as an increase of 2 or more points in at least 2 YMRS items or clinician judgment), we will discontinue treatment and adjust anti-manic medication and, if necessary, add on other pharmacologic measures (neuroleptics, benzodiazepines) as clinically indicated with the intent to treat until remission is achieved.

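### Section 8 takes participants out of the study, not just off stimulation, for worsening and similar reasons, so the visit that defines the primary endpoint is not scheduled for them

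*Combined protocol and SAP*

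**What the plan says.** Section 8 carries a heading about discontinuing the intervention. Its operative sentence goes further: "Study doctors are to discontinue participants from the study if participants" meet any of a list of conditions. Three of these can follow from a poor course:

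- "In the Investigator's opinion, is experiencing a clinically significant deterioration"
- "Experience a serious or intolerable adverse event that prevents the participant from continuing"
- "Conduct a protocol violation, including lack of compliance"

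Section 7.2 uses similar language for a suspected seizure: "participation will be discontinued and the participants will be provided with a referral to outpatient care".

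For what happens next, Section 8 says that "the reason(s) for discontinuation are to be recorded by the study", that participants return to their usual care team and, where withdrawal is related to treatment, that "they will be followed until the event(s) have resolved or no further action is required". It mentions no MADRS or YMRS rating.

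The mania rules differ. Section 5.1 says "we will discontinue treatment and adjust anti-manic medication", and Sections 6.2, 7.1 and 7.2 likewise stop stimulation or treatment without ending participation. Section 8 does not say how it relates to them.

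Section 9.3.1 defines the primary outcomes, MADRS and YMRS, as change from baseline to the immediate post-treatment assessment, up to 5 days after the last treatment day. Section 9.4 plans generalized linear mixed models. Section 9 names no analysis set, no missing-data rule and no sensitivity analysis.

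**The concern.** A participant who leaves the study under Section 8 has no scheduled visit at the time point that defines the primary endpoint. Worsening is both a bad result on that endpoint and a reason for removal, so whether the endpoint is observed depends in part on how the participant is doing.

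A mixed model copes with missing visits if the chance of missingness depends only on ratings that are observed and modelled, and if the model is adequate. Removal here can rest on the investigator's opinion, which need not be reflected in an earlier rating.

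There are ten participants and no comparison group. One or two removals can therefore move the estimate noticeably, and nothing inside the study would reveal it. The Abstract and Section 9.1 say that the results are meant to motivate a larger trial, so a flattering estimate would carry forward.

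**Working it through.** **Step 1. Is the endpoint visit scheduled anywhere for these participants?**

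- Section 8: reason recorded, return to usual care, event follow-up if treatment-related. No outcome rating.
- Section 7.4: adverse events followed to resolution or transfer of care. This is safety follow-up, not outcome measurement.
- Section 6.2, Follow-up: sets visit windows from the last treatment day for those who complete treatment in fewer than five days. Treatment stops at MADRS of 10 or less, so this clearly fits early remitters. It does not say that people removed under Section 8 return.

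So no section schedules it.

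**Step 2. The plan's own figures.** Two sites x 5 = 10 participants, which agrees with the Synopsis. No power, precision, SD or dropout rate is stated, so every rate and score change below is an assumption.

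**Step 3. Chance that the problem arises.** With removal rate p per participant, P(at least one of 10) = 1 - (1 - p)^10.

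| Assumed p | P(at least one) |
|---|---|
| 5% | 40% |
| 10% | 65% |
| 20% | 89% |

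**Step 4. Shift in the raw mean.** Let c be the mean change in completers, d the change in those removed and k the number removed. The mean in all ten is ((10 - k)c + kd)/10. Completers alone give c. The difference is k(c - d)/10.

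| c | k | d | All ten | Completers only | Difference |
|---|---|---|---|---|---|
| -20 | 1 | 0 | -18.0 | -20 | -2.0 |
| -20 | 1 | +5 | (9 x -20 + 5)/10 = -17.5 | -20 | -2.5 |
| -20 | 2 | +5 | (8 x -20 + 10)/10 = -15.0 | -20 | -5.0 |
| -15 | 1 | 0 | -13.5 | -15 | -1.5 |
| -15 | 1 | +5 | -13.0 | -15 | -2.0 |
| -15 | 2 | +5 | -11.0 | -15 | -4.0 |

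Each removal is worth roughly 1.5 to 2.5 MADRS points in these scenarios. This is a raw completer comparison, not the planned model.

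**Step 5. Would a mixed model with daily scores repair it?** A simulation of 300 trials of 10 people assumed baseline mean 30 (SD 4), daily slope -3 (SD 2.5), residual SD 3 and exit at a 5-point rise from baseline, with one rating a day. Scores up to and including the one that triggered exit were kept. On average 1.2 people left per trial.

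| Analysis | Mean change |
|---|---|
| All ten, endpoint collected | -15.3 |
| Completers only | -18.0 |
| Random-intercept mixed model, daily scores to exit | -17.2 |

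The bias fell from 2.7 points (18.0 - 15.3) to 1.9 (17.2 - 15.3). Exit here depended only on observed scores, so the remaining 1.9 points cannot be put down to unrecorded worsening. It is consistent with fitting a random intercept to data generated with varying slopes. A random intercept implies compound symmetry, one of the two structures that Section 9.4 names. The result shows that daily scores help without necessarily curing the problem. It does not estimate the bias in this trial.

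**The case against.** The strongest reply is that pre-exit data are rich. Section 6.2 takes MADRS morning, evening and as clinically indicated, and YMRS morning and evening. Section 6.3 describes the daily and follow-up MADRS together as the primary outcome measure, and Section 9.4 plans a repeated-measures model. A participant who worsens during treatment may well be rated before leaving, and those scores could be used. This stands as mitigation. It is not a guarantee: Section 9.4 does not say that daily scores are modelled, and Section 9.3.1 ties the endpoint to a visit that these people do not have. Section 9.4 also adjusts for days to remission, which has no value for someone who never remits. A fit restricted to complete covariates would drop that person's daily scores too.

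A reader might infer three stronger things that the documents do not support:

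- **That a completer-only analysis is planned.** No section plans one.
- **That mania will be understated.** Emergent mania stops treatment, not participation, in Sections 5.1, 6.2, 7.1 and 7.2. Adverse events are reported and followed, and unresolved hypomania counts towards the stopping rule in Section 9.2. Mania ratings are lost only if Section 8 is applied as well.
- **That any adverse event leads to removal, or that a response rate would be inflated.** The adverse-event trigger is narrow, and response rate is not an outcome in Section 9.3.

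It is also fair that this is a feasibility pilot with no power claim, that the endpoint window is short, and that no wording recovers people who withdraw consent or cannot be reached.

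**Conclusion.** The point holds as a flaw in a stated rule. If Section 8 is followed as written, the primary-endpoint visit is not scheduled for participants removed for worsening, for a serious or intolerable adverse event that prevents continuing, or for protocol violation. For the first two in particular, that loss is related to poor outcome. The likely direction favours treatment on MADRS.

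The size cannot be known, because no dropout rate is given and it is unclear whether daily scores enter the model. Assuming completers improve by 15 to 20 points and those removed change by 0 to +5, each removal shifts the raw mean by about 1.5 to 2.5 points. Modelling the daily scores would reduce this. It would be wrong to state as fact that efficacy will be overstated: with no removals there is no bias from this source.

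The change is worth making before analysis because it is cheap and ten uncontrolled participants leave little room to absorb a loss.

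**What to change.** - **Section 8:** separate stopping stimulation from leaving the study. State that a participant who stops stimulation, for whatever reason, is still asked for the immediate and 1-month MADRS, YMRS and adverse-event assessments unless consent for follow-up is withdrawn. Section 6.2 already permits remote follow-up. The Section 6.1 schedule marks adverse-event monitoring on treatment days only, so it needs a matching entry.
- **Consistency:** reconcile Section 8 with the mania wording in Sections 5.1, 6.2, 7.1 and 7.2, the seizure wording in Section 7.2 and the early-completion windows in Section 6.2, so that each says whether treatment or participation ends and whether ratings continue.
- **Section 9.4:** define the analysis set as everyone who received any stimulation, state that their daily scores are included, and say how the days-to-remission covariate is handled for those who do not remit, so that they are not dropped. Add a short missing-data sensitivity analysis.

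The clinical triggers for stopping stimulation stay as they are. The cost is protocol wording and at most two extra remote visits per affected person. The reported effect may look less favourable.
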